Before the subject undergoes procedures specific to the protocol, the informed consent and HIPAA authorization will be signed and dated by the subject and the member of the study team performing the Informed Consent procedures. Following referral and notification that a patient meets initial pre-screening criteria, the PI and/ member of the study team will present the option to participate in the research study to the patient and any family/ friend that the patient wishes to include. Study subjects will be recruited by study staff (PI, co-investigator, research nurse/coordinator) from patients who present for Coronary Artery Bypass Surgery once it is deemed appropriate to approach patient per good clinical practice guidelines. If the patient expresses interest, then the informed consent, HIPAA authorization (including risks and benefits) will be discussed in detail and an opportunity will be provided to ask questions. Patient will also be provided the opportunity to discuss with family/ friend, as he/she deems fit. After all required signatures have been obtained; a copy of the consent and HIPAA authorization will be provided to the subject and scanned into the subject's medical record.

18. DOCUMENTATION OF INFORMED CONSENT:

Following the study subjects' enrollment a research enrollment note documenting the procedure of informed consent will be entered in CPRS by a member of the research team. Notes will include a brief description of the study, procedures for obtaining consent and HIPAA authorization, study personnel and contact numbers. A copy of the signed informed consent and HIPAA authorization form will be provided to the research office for scanning into the patient's records.

19. PAYMENT TO SUBJECTS FOR THEIR PARTICIPATION:

Study participants will be paid \$50 for 1 month and 6 month, and \$200 for 12 month follow-up visits, to assist with the cost of transportation.

20. PROVISIONS FOR DATA STORAGE AND CONFIDENTIALITY:

Confidentiality of subject data will be maintained in accordance with VA, IRB and HIPAA regulations. Physician investigators, study coordinators and study team members will have access to the subjects' medical records and the results of all examinations undertaken.

In accordance with HIPAA, the consent form and HIPAA authorization describes to the subject what protected health information will be obtained and/or stored and for what purpose, as well as a list of who may have access to this data, including outside agencies. All records will be maintained in a locked cabinet in the research team's locked office in the CRU. Computerized data will be de-identified and stored on a password protected computer in a locked office of the research team. Additionally patient logs and identifiable computerized data will be stored on the study team's limited access shared research folder located on the secure VA server.

In accordance with VA guidelines, all records of this research study will continue to be securely maintained in accordance with VHA Record Control Schedule. The records will be kept in a locked file cabinet or locked room with limited access. If the PI leaves the VA facility, the research records will be retained by the institution.

21. PROVISIONS FOR STORAGE/ ANALYSIS OF RESEARCH SPECIMENS:

Not Applicable.

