INVESTIGATOR'S ABBREVIATED PROTOCOL

1. TITLE: Prasugrel for prevention of early saphenous vein graft thrombosis

2. PRINCIPAL INVESTIGATOR: [name], PhD

CO-INVESTIGATOR: [name]

KEY MEMBERS: [name]

[name]

[name]

[name]

[name]

[name]

[name]

[name]

3. SPONSOR OF THE STUDY: VA Merit, VA OR&D

4. IND/ IDE: Not Applicable

5. PURPOSE OF THE STUDY, INCLUDING HYPOTHESIS TO BE TESTED:

Aortocoronary saphenous vein graft failure is common and is associated with high morbidity and mortality. Thrombus formation plays a critical role in early saphenous vein graft occlusion and may predispose to subsequent atherosclerosis formation. Optical coherence tomography is a novel, high-resolution, intravascular imaging technique that can reliably identify thrombus. Based on the findings of earlier VA Cooperative Studies, aspirin significantly reduces the incidence of early saphenous vein graft failure and is currently used in nearly all patients undergoing coronary bypass graft surgery. Administration of clopidogrel for improving early saphenous vein graft patency has provided conflicting results in small randomized studies. Prasugrel is a novel thienopyridine that provides more rapid, consistent, and intense platelet inhibition than clopidogrel. However, in patients who undergo coronary artery bypass graft surgery, it remains unknown whether prasugrel may decrease thrombus formation in saphenous vein grafts during the first postoperative year, and whether this will result in less saphenous vein graft wall thickening, less lipid deposition in the saphenous vein graft wall and fewer clinical events without increasing the risk for severe bleeding.

We hypothesize that in patients undergoing clinically-indicated coronary artery bypass graft surgery, administration of prasugrel starting at dismissal from the index coronary bypass graft surgery hospitalization will result in lower prevalence of thrombus formation in a target SVG, as assessed by optical coherence tomography performed 12 months post surgery compared to placebo, with similar incidence of major bleeding.

6. BACKGROUND AND RESULTS OF PREVIOUS RELATED RESEARCH:

Saphenous vein graft failure

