Limet et al randomized 173 patients to ticlopidine vs. placebo and performed graft angiography at 3 time points (10, 180, and 360 days).²⁹ Graft patency was higher in the ticlopidine group at all time points.

Two Chinese studies have been published (the first author is Gao in both studies):

Gao et al randomized 197 patients to aspirin + clopidogrel vs. aspirin alone. Using computed tomography they reported similar 1 and 12-month SVG patency rate (98.1% and 98.2% at 1 month and 93.5% and 96.3% at 12 months for aspirin and the combination, respectively, p=non-significant).³⁰

Gao et al randomized 249-patients to aspirin + clopidogrel vs. aspirin alone. Using computed tomography they reported higher 3-month SVG patency rate in patients receiving clopidogrel (91.6% vs. 85.7%, p=0.043).³¹

In contrast, the Clopidogrel After Surgery for Coronary Artery Disease (CASCADE) trial randomized 113 patients to aspirin + clopidogrel vs. aspirin + placebo for 1 year. Follow-up angiography and IVUS evaluation showed no difference in 12-month SVG patency (95% in both groups, p=1.0) or in SVG intimal area hyperplasia ($4.5 \pm 2.1 \text{ mm}^2$ vs. $4.1 \pm 2.0 \text{ mm}^2$, p=0.44).¹²

Finally, the Preoperative Aspirin and Postoperative Antiplatelets in Coronary Artery Bypass Grafting (PAPA-CABG) study randomized 100 patients undergoing CABG to placebo or clopidogrel for 30 days. Patients subsequently underwent computed tomography for bypass graft patency evaluation.³² Overall, similar proportion of patients in the placebo and clopidogrel group had at least one SVG occlusion (23.1% vs. 17.5%, p=0.54), but radial artery occlusion occurred less frequently in the clopidogrel group (43.8% vs. 10.5%, p=0.05). Although more potent antiplatelet therapy could increase the risk of bleeding, no significant difference in bleeding was observed in the above studies, yet these studies were underpowered to detect such differences.

Table 1. Studies assessing the effect of thienopyridine administration post CABG on bypass graft patency.

Study	Thienopyridine	N	Time of assessment	Primary endpoint	Findings
Limet et al ²⁹	ticlopidine	173	10, 180, and 360 days	Graft patency, as assessed by coronary angiography	Higher graft patency in the ticlopidine group at day 10 (84.4% vs. 66.7%, p < 0.05), day 180 (74.4% vs. 52.3%, p < 0.05) and day 360 (75.0% vs. 52.5%, p < 0.05).

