Approximately 120 patients will be randomized into this study at the Dallas VA Medical Center.

10. JUSTIFICATION FOR THE USE OF SPECIAL SUBJECT POPULATIONS:

Not applicable.

11. STUDY DESIGN:

The primary efficacy objective is to compare the prevalence of SVG thrombus as detected by optical coherence tomography of a target SVG between patients receiving prasugrel vs. placebo. We hypothesize that prasugrel will be superior to placebo in reducing the prevalence of SVG thrombus at 12-month follow-up OCT imaging.

The primary safety endpoint is the incidence of severe bleeding as defined using the GUSTO study criteria.⁶⁷ We hypothesize that patients receiving prasugrel will have similar incidence of severe bleeding compared to patients receiving placebo during the 12-month study period.

The secondary endpoints will be: (1) incidence of angiographic SVG failure (defined as $\geq 75\%$ SVG diameter stenosis in at least one SVG); the total and normalized total SVG atheroma volume within at least 40 mm of the target SVG, as assessed by intravascular ultrasonography; the lipid core burden index of the target SVG, as assessed by near-infrared intracoronary spectroscopy; and (2) the incidence of major adverse cardiac events and moderate bleeding during the 12-month study period.

The proposed study is a phase 3, single-center, randomized, double-blind, controlled, parallel-group study of prasugrel vs. matching placebo in patients with recent CABG, starting at the time of hospital dismissal from CABG (Figure 13). All patients will be receiving aspirin, as per standard current practice.

[figure not shown]

Figure 13: Flowchart of the proposed study design.

CABG = coronary artery bypass graft surgery; OCT = optical coherence tomography; IVUS = intravascular ultrasound; NIRS = near-infrared spectroscopy; R = randomization; m = month; FU = follow-up.

12. DESCRIPTION OF PROCEDURES TO BE PERFORMED:

The study design will be explained to the patients and if they agree to participate they will be asked to sign an informed consent form and they will receive a copy of the consent form. They will subsequently be randomized to prasugrel or placebo, as described below.

Randomization and Treatment

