The prevalence of thrombus within the target SVG at 12-month OCT imaging (primary efficacy endpoint) will be analyzed using the Fisher's exact test. In view of the relatively small sample size of the trial, multivariable logistic regression analyses will be performed to adjust the findings for any potential differences in the baseline characteristics of the two study groups, which are known to influence the occurrence of SVG failure. Such characteristics are: patient age, prior myocardial infarction; total cholesterol and HDL-cholesterol levels; minimum graft diameter; mean arterial pressure; ejection fraction; male gender; and current smoking.⁶⁹ The significant characteristics will be incorporated in the calculation of an adjusted odds ratio representing the association between treatment and the prevalence of thrombus, along with 95% confidence intervals. Because off-pump and endoscopic SVG harvesting may be associated with higher rates of SVG failure, randomization will be stratified by (a) on vs. off pump and (b) endoscopic vs. open harvesting.

The time elapsed to the incidence of severe bleeding, defined using the GUSTO criteria⁶⁷ (primary safety endpoint) will evaluated using Kaplan-Meier survival curves and compared between the 2 study groups using the log-rank test.

Statistical Analysis of secondary endpoints:

The differences in angiographic SVG failure, in total and normalized total SVG atheroma volume and in lipid core burden index at 12-month SVG imaging will be compared between the 2 study groups using Fisher's exact test. A logistic regression model will be developed to evaluate the treatment effect on this outcome adjusting for patient age, prior myocardial infarction; total cholesterol and HDL-cholesterol levels; minimum graft diameter; mean arterial pressure; ejection fraction; male gender; and current smoking.⁶⁹

The incidence of major adverse cardiovascular events (composite of death, acute coronary syndrome, and coronary revascularization) at 12 months will be compared between the two study groups using the chi-square test. Kaplan-Meier survival curves and the log-rank test will be used to compare time-to-event of major adverse cardiac events in the two study groups.

All tests will be two-sided. The critical level for the primary and four secondary outcomes will be 0.05. No adjustments will be made for multiple secondary endpoints

14. PROVISIONS FOR MANAGING ADVERSE REACTIONS:

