For safety monitoring, any emergency adverse event resulting from participation in the study will be treated at the Dallas VA Medical Center. [name] will evaluate all adverse events and determine the appropriate course of action.

If a patient develops severe bleeding during the study period, prasugrel will be temporarily held and will be discontinued if the patient is considered to be at increased risk for recurrent bleeding. If a patient develops an indication for receiving oral anticoagulation therapy with warfarin or dabigatran during his or her participation in the study, prasugrel administration will be discontinued to minimize the risk of bleeding.

If any subjects are hospitalized for an acute coronary syndrome or undergo coronary angiography at an outside hospital, the hospitalization records will be obtained and reviewed by the clinical events committee. The Universal definition of myocardial infarction will be used for diagnosing myocardial infarction. Bleeding will be assessed with the use of the GUSTO criteria.⁶⁷ Severe bleeding will be defined as fatal bleeding, intracranial hemorrhage, or bleeding causing hemodynamic compromise requiring blood or fluid replacement, inotropes, or surgery.⁶⁷ The frequencies of moderate bleeding, defined as bleeding requiring transfusion not characterized as severe, and moderate/severe and severe bleeding will also be analyzed. Information on (surgical or percutaneous) coronary revascularization will also be collected. Data will be entered on paper-based case report forms and will be double-entered into a secure, password protected database, accessible only by study personnel. Subjects will be identified by a unique study number in the database.

Additionally a Data Safety Monitoring Board will be appointed to review the study periodically (every 12 months, or sooner if required).

15. RISK/ BENEFIT ASSESSMENT:

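### The primary safety hypothesis is that severe bleeding is similar, but the planned two-sided log-rank test cannot support similarity, and no between-arm estimate or interval for bleeding is planned

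*Combined protocol and SAP*

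**What the plan says.** Section 5 hypothesizes less graft thrombus on prasugrel "compared to placebo, with similar incidence of major bleeding", and names as an open question whether there will be "fewer clinical events without increasing the risk for severe bleeding". Section 11 makes GUSTO severe bleeding the primary safety endpoint, with the hypothesis that "patients receiving prasugrel will have similar incidence of severe bleeding compared to patients receiving placebo". So section 5 speaks of major bleeding in its hypothesis and section 11 of severe bleeding.

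Section 13 (primary endpoints) describes time to severe bleeding by Kaplan-Meier curves, "compared between the 2 study groups using the log-rank test". All tests are two-sided at 0.05. Section 14 defines the GUSTO categories and says the frequencies of moderate "and moderate/severe and severe bleeding will also be analyzed", without naming a method.

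The one effect estimate with an interval in section 13 is for efficacy: an adjusted odds ratio for the "association between treatment and the prevalence of thrombus, along with 95% confidence intervals". Sample size and power in section 13 concern thrombus only. No expected bleeding rate and no margin for similarity appear anywhere.

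On earlier thienopyridine trials, section 6 says that "no significant difference in bleeding was observed in the above studies, yet these studies were underpowered to detect such differences". Table 1 lists those trials at 100 to 249 patients. This trial randomizes about 120.

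**The concern.** The null hypothesis of a log-rank test is equal event-time distributions. A significant result contradicts similarity. A non-significant result only fails to contradict it, and with few events that is the likely result whether or not prasugrel causes more bleeding. The stated hypothesis and its only specified test therefore do not fit each other.

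A between-arm difference with an interval would say how large an excess the data still allow. None is planned for harm, although one is planned for benefit. At the end of the trial a reader would have to derive it from the counts. The protocol makes this same criticism of the earlier trials, most of which were about as large as this one or larger.

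**Working it through.** **Inputs from the documents.** About 120 randomized 1:1, so 60 per arm; 12 months of follow-up; intention to treat; two-sided 0.05.

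**Input assumed.** A 12-month placebo risk of severe bleeding of 1% to 5%, because the documents give none.

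**1. The plan's own figure (efficacy).** For 25% versus 5%, 80% power and two-sided 0.05, the normal-approximation sample size is 49 per group with pooled variance and 47 unpooled; the plan states 48. Dropout: 48 / 0.8 = 60. With 48 per group and an 80% relative reduction, power at control prevalences of 20%, 25% and 30% is 68.0%, 79.3% and 87.7%, against the stated 67%, 80% and 89%. The sizing reproduces closely, and it does not involve bleeding.

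**2. Events needed to detect a bleeding excess.** Schoenfeld: events = 4(1.960 + 0.842)² / (ln HR)².
- HR 2: 31.4 / 0.480 = 65.4, so 66 events.
- HR 3: 31.4 / 1.207 = 26.0, so 27 events.

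Expected events under a doubled hazard: 60 × (0.010 + 0.0199) = 1.8 at a 1% placebo risk, and 60 × (0.050 + 0.0975) = 8.9 at 5%.

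**3. Simulated log-rank power.** 60 per arm, exponential times, no loss before 12 months:

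| Placebo vs prasugrel risk | Power |
|---|---|
| 1% vs 2% | about 2% |
| 2% vs 4% | about 7% |
| 5% vs 10% | about 17% |
| 1% vs 5% | about 20% |
| 2% vs 10% | about 45% |
| 2% vs 15% | about 78% |
| 2% vs 20% | about 94% |

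With 20% exponential dropout the three doublings give about 1%, 6% and 16%. That is a further assumption: the plan's 20% allowance raises 48 evaluable patients to 60 in the thrombus calculation and is not stated as loss to bleeding follow-up.

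**4. What an interval would show.** Newcombe's method takes the Wilson limits (l, u) of each arm:

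lower = d − √[(p₁ − l₁)² + (u₂ − p₂)²]

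upper = d + √[(u₁ − p₁)² + (p₂ − l₂)²]

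- **0/60 vs 0/60.** Each Wilson upper limit is 3.84 / (60 + 3.84) = 6.0%. The difference is 0 (−6.0 to +6.0 points).
- **1/60 vs 1/60.** Wilson limits are 0.3% and 8.9%. The difference is 0 (−7.3 to +7.3).
- **5/60 vs 1/60.** Wilson limits for 5/60 are 3.6% and 18.1%. The difference is +6.7 (−1.9 to +16.5), with log-rank p 0.09 to 0.10 depending on event order.
- **4/60 vs 0/60.** The difference is +6.7 (−0.6 to +15.9), with log-rank p 0.043.

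**5. Should the interval replace the test?** In the same simulations the Newcombe interval excludes zero less often than the log-rank test rejects: about 11% against 20% of trials at 1% vs 5%, and about 40% against 45% at 2% vs 10%.

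A crude proportion also counts early dropouts as event-free. Write λ = −ln(1 − p) and δ = −ln 0.8. The observed proportion is then [λ/(λ + δ)] × [1 − exp(−(λ + δ))], which turns 2% vs 10% into 1.79% vs 8.98%. The difference falls from 8.0 to 7.2 points. The interval should therefore be added beside the test, and based on Kaplan-Meier estimates where it can be.

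**6. Arms without events.** The usual Kaplan-Meier (Greenwood) variance is zero in such an arm. With equal risks, P(at least one empty arm) = 1 − (1 − (1 − p)⁶⁰)². This is 79% at 1% and 51% at 2%, so a fallback interval has to be named.

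**The case against.** **The outputs already planned are enough.** Kaplan-Meier curves give cumulative incidence by arm and section 14 adds frequencies, so it would be wrong to infer that the safety result is a bare p-value. That stands. The gap is narrower: none of these outputs is a between-arm contrast with an interval.

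**Similar is meant informally, and nobody claims equivalence.** A reader might infer that a non-significant result will be presented as proof of similar bleeding. The documents do not say so; they are silent on how it will be reported, and section 6 shows that the authors understand the problem. But similarity is written as the hypothesis for a named primary safety endpoint, so the mismatch does not depend on guessing intent.

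**The size is assumed.** True. The documents give no bleeding rate, and a very large excess would probably be detected (about 78% power at 2% vs 15%, about 94% at 2% vs 20%). The test is insensitive to moderate excesses, not to every excess.

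**The log-rank test should not be demoted.** This stands fully. Making an interval on crude proportions primary would flag harm less often and would ignore censoring.

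**The attached sponsor's protocol may cover this.** It may. It was not available, and this document is titled abbreviated. Section 13 nevertheless specifies tests, covariates and significance level.

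**Conclusion.** The point holds. The plan states similar bleeding as a hypothesis, specifies only a test that cannot support it, and plans no between-arm estimate or interval for bleeding.

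The non-support follows from the test itself and needs no assumed rate. The size does need one: at assumed placebo risks of 1% to 5%, a true doubling would be non-significant in roughly 83% to 98% of trials of this size, and even a trial with no events would leave about 6 points either way.

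Two stronger readings are not supported. The documents do not show that the trial must be enlarged or given a non-inferiority margin. They set none, and an illustrative 5-point margin (80% power, one-sided 0.025) would need 63 to 299 per arm at true risks of 1% to 5%, so estimation is the realistic aim. Nor do they show that the log-rank test is wrong as a check for harm. It should stay.

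**What to change.** **Section 13.** Keep the log-rank test as planned and add:

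> The difference between arms (prasugrel minus placebo) in 12-month cumulative incidence of GUSTO severe bleeding, from the Kaplan-Meier estimates, will be reported with a 95% confidence interval, with event counts and numbers censored before 12 months by arm. If an arm has no events, a Newcombe interval for the difference in proportions will be given. The same will be reported for moderate-or-severe bleeding. A non-significant log-rank result will not be interpreted as showing similar bleeding.

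**Section 11.** Replace the safety hypothesis sentence with:

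> The safety objective is to estimate the difference in the incidence of severe bleeding between prasugrel and placebo during the 12-month study period; the trial is not sized to show that bleeding is similar.

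**Section 5.** Replace "with similar incidence of major bleeding" with a separate sentence giving the same objective for GUSTO severe bleeding. This also removes the major/severe discrepancy.

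**Cost.** Wording in three sections and two interval calculations; no new data, margin or patients. The safety conclusion becomes weaker than similar, and the intervals will be wide. At low event rates the Newcombe fallback will be used often, and it treats dropouts as event-free, which is why censoring is shown by arm. Interval and test can disagree near the boundary (4/60 vs 0/60 above), so both are reported and a significant log-rank result still counts as a harm signal.

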Randomization will be performed based on computer-generated random numbers, and will be blocked with block sizes of 4-10, varying randomly. Subjects will be assigned on a 1:1 basis to prasugrel (Effient®, Daiichi Sankyo and Eli Lilly) at a dose of 10 mg daily or matching placebo. The patients and study coordinators will be blinded to the study medication. Angiographic, OCT, IVUS, NIRS and angiographic analyses will also be done blinded to study-arm allocation. Breaking the blind will be possible for any patient who develops a complication or whose clinical care requires knowledge of the study group allocation.

Patients randomized to the treatment arm will receive prasugrel at a dose of 10 mg daily. Patients randomized to placebo will receive one placebo tablet. To minimize the potential for side effects during the study period patients with an increased risk of bleeding [need for warfarin or oral Xa inhibitor or thrombin inhibitor administration, recent (within 30 days) major bleed, known bleeding diathesis or coagulation disorder], will be excluded from the present study.

To minimize the possibility of study medication discontinuation, adherence with the study medication will be assessed during every follow-up visit. Patients will be asked to return all unused medications and study containers. The number of tables issued minus the number of tablets returned will be used to calculate the number of tablets taken. From this information compliance will be calculated as: (number of capsules dispensed – number of capsules returned) / (number of days between visits x number of tablets per daily dose). Patients with <80% compliance with the study medication will be counseled on the importance of taking their medications.

Catheterization, OCT, IVUS, and NIRS

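### A complication alone is enough to break the blind, and the plan does not say who classifies bleeding or whether they are blinded, so the primary safety endpoint is open to classification with the arm known.

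*Combined protocol and SAP*

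**What the plan says.** Section 11 describes the design: "The proposed study is a phase 3, single-center, randomized, double-blind, controlled, parallel-group study of prasugrel vs. matching placebo". It also sets the safety objective: "The primary safety endpoint is the incidence of severe bleeding as defined using the GUSTO study criteria", with the hypothesis that the two arms will be similar over 12 months. Moderate bleeding is a secondary endpoint.

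Section 12, under Randomization and Treatment, gives the blinding detail in three statements:

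- People: "The patients and study coordinators will be blinded to the study medication".
- Assessments: "Angiographic, OCT, IVUS, NIRS and angiographic analyses will also be done blinded to study-arm allocation".
- Code break: "Breaking the blind will be possible for any patient who develops a complication or whose clinical care requires knowledge of the study group allocation".

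Section 14 covers events. One study role "will evaluate all adverse events and determine the appropriate course of action". A clinical events committee is mentioned once, to review records of acute coronary syndrome admissions and of angiography at outside hospitals. The definition reads: "Severe bleeding will be defined as fatal bleeding, intracranial hemorrhage, or bleeding causing hemodynamic compromise requiring blood or fluid replacement, inotropes, or surgery". Moderate bleeding is bleeding that needs transfusion and has not been called severe. GUSTO is to be used, but no one is named as applying it.

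Section 13 analyses time to severe bleeding with Kaplan-Meier curves and the log-rank test.

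**The concern.** The code-break rule joins two grounds with an 'or'. The second, clinical need, is the usual one. The first is satisfied by any complication, with no threshold of severity, no approver, no limit on who learns the allocation and no log. A bleed is a complication, so the events that make up the primary safety endpoint are exactly the ones for which the blind may be lifted.

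That would matter less if the grading of bleeds were clearly protected, but the plan does not say that it is. Fatal and intracranial bleeds leave little room for opinion. The third route to a severe grade, hemodynamic compromise requiring intervention, does call for judgement, and moderate bleeding is defined partly as what was not called severe. If the arm is known when that call is made, grading can differ by arm. Because the hypothesis is similar severe bleeding, a tendency to grade prasugrel-arm bleeds down would favour the expected conclusion.

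**Working it through.** **Step 1. Which events qualify for a code break.** The rule in section 12 is (complication) or (care requires the allocation). Severe bleeding under section 14 is always a complication, so the first ground is met every time. All severe bleeds are therefore eligible. This says nothing about how often the blind would actually be broken.

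**Step 2. Who is stated to be blinded.**

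| Role or assessment | Where it appears | Blinding stated? |
|---|---|---|
| Patients, study coordinators | Section 12 | Yes |
| Angiographic, OCT, IVUS and NIRS analyses | Section 12 | Yes |
| Role that evaluates adverse events | Section 14 | No |
| Clinical events committee | Section 14 | No; bleeding is not assigned to it |
| Person who applies GUSTO to bleeds | Not named | No |

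The DSMB in section 16 reviews aggregate adverse events periodically. It is not given the task of adjudicating single events.

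**Step 3. How many events to expect.** The documents give no severe-bleeding rate. Assuming 1% to 5% per arm over 12 months, 60 patients give 60 × 0.01 = 0.6 to 60 × 0.05 = 3 events per arm.

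**Step 4. What one regraded event can do.** The plan has no figure of its own to reproduce here. The illustration uses the planned log-rank test with 60 per arm, no censoring, no tied times and all k events in the prasugrel arm. At the event after j earlier ones, the expected count in the prasugrel arm is (60 − j)/(120 − j) and the variance is (60 − j) × 60/(120 − j)². The statistic is (k − E)²/V on 1 degree of freedom, with E and V the sums over j = 0 to k − 1.

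- 4 vs 0: E = 0.5000 + 0.4958 + 0.4915 + 0.4872 = 1.9745; V = 0.2500 + 0.2500 + 0.2499 + 0.2498 = 0.9997; (4 − 1.9745)²/0.9997 = 4.10; p = 0.043.
- 3 vs 0: E = 0.5000 + 0.4958 + 0.4915 = 1.4873; V = 0.7499; (3 − 1.4873)²/0.7499 = 3.05; p = 0.081.

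Moving one prasugrel-arm event from severe to moderate takes the result across 0.05.

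**Step 5. Sensitivity to the counts and the test.** By log-rank, 6 vs 0 (p = 0.012) and 5 vs 0 (p = 0.023) are both below 0.05, so one regraded event does not cross the line there. Fisher's exact test puts the crossing between 6 vs 0 (p = 0.027) and 5 vs 0 (p = 0.057), but the plan uses that test for thrombus, not for severe bleeding. The crossing point depends on the test; under either test one event can be decisive.

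**The case against.** The strongest reply is that silence is not a statement of open-label assessment. The trial is labelled double-blind with matching placebo, and the list in section 12 is not said to be complete. A reader might infer that the event evaluators know the arm. The documents do not say so; they only fail to say that these roles are blinded. This reply stands and limits the wording of the point.

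A reader might also infer that the role evaluating adverse events is the one grading bleeds. Section 14 gives that role evaluation and management of adverse events and does not connect it to GUSTO. The grader is unnamed, which is the gap.

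The code break is described as possible, not required, and nothing says that the allocation would reach whoever grades the event. That is fair. But discretion without criteria, restriction or a log leaves no means of showing afterwards that grading was blinded.

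The harm is bounded. The OCT reading for the primary efficacy endpoint is blinded. Section 14 also plans an analysis of moderate and severe bleeding together, which a shift between those grades would not alter. A bleed that needed fluid but no transfusion, however, would fall out of both grades if not called severe.

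Section 14 says of a severe bleed: "prasugrel will be temporarily held and will be discontinued if the patient is considered to be at increased risk for recurrent bleeding". Section 12 (Catheterization, OCT, IVUS, and NIRS) likewise speaks of continuing prasugrel after early angiography. A reader might infer that the site must know the arm to apply these rules. The more natural reading is that prasugrel is shorthand for study medication, the term used elsewhere in section 12. This is a wording inconsistency, not evidence of unblinding.

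Finally, this is an abbreviated protocol that points to an attached sponsor's protocol not available here. Code-break and adjudication procedures may be set out there.

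**Conclusion.** The concern holds in limited form. On the stated rule every severe bleed is eligible for unblinding without clinical need, and the plan identifies neither the person who grades bleeds nor their blinding. It does not show that evaluators are unblinded, or that codes will be broken often.

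One regraded event could change the safety result: 4 vs 0 gives p = 0.043 and 3 vs 0 gives p = 0.081 by the planned test. Those counts are assumed, as are 60 followed per arm, no censoring and no ties. A split of 4 vs 0 lies slightly above the 0.6 to 3 events per arm expected at an assumed rate of 1% to 5%, so it shows sensitivity and is not a forecast. No sample size or efficacy figure is affected. This is a cheap improvement to make before events are classified, because the blinding of a judged event cannot be reliably restored later.

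**What to change.** In section 12, Randomization and Treatment:

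1. Make clinical need for the allocation the only ground for a code break, so that a complication alone is not sufficient.
2. Limit disclosure to the treating clinician, and log each break with its date and reason.

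In section 14:

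3. State that bleeding and cardiac events are classified blinded to arm, by existing study roles or by the clinical events committee, and that any code break is withheld from those classifying.

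Separately, reconcile the use of prasugrel in section 12 (early angiography) and section 14 with the term study medication, so that the text reads the same in both arms. This should change no clinical rule.

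If the sponsor's protocol already contains these provisions, a cross-reference is enough. The cost is protocol wording and a short log. Emergency unblinding for care stays available; the small downside is that clinicians will not learn the allocation when care does not need it.
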